7.1.4. Shifts in Prednisone Average Daily Dose from Baseline

Shifts from average daily dose category at baseline will be summarised using frequencies and percentages, and be presented by the parent randomised treatment group and the total Safety population, for each visit.

Categories reported as [1] No prednisone use (0 mg prednisone equivalent)

¹ Records to be collapsed.

²Ongoing concomitant medications (CM) in the parent study BEL112341 were entered by site in the BEL114333 eCRF. Ongoing CMs in the parent study BEL113750 were programmatically added to the BEL114333 data transfer.

- [2] > 0 to ≤ 7.5 mg prednisone equivalent
- [3] > 7.5 to ≤ 40 mg prednisone equivalent
- [4] > 40 mg prednisone equivalent
- [5] Unknown

No imputation will be performed for missing data.

7.1.5. Extent of Exposure and Study Drug Administration

- The extent of exposure to IV belimumab treatment through end of study will be assessed by examining the duration of exposure to belimumab in days and the total number of infusions a subject received. First and last infusion dates will be used, regardless of any intermittently missed infusions.
- Duration of exposure to IV belimumab (in days) will be calculated for each subject, as:

Extent of Exposure (days) =

Date of last exposure to IV treatment +28 – Date of first exposure to IV treatment where

- the first IV belimumab dose either occurred during the parent study BEL113750 (for subjects randomized to belimumab in BEL113750) or during BEL114333 (for everyone else).
- the last IV belimumab dose occurred during BEL114333 for everyone. For any subjects who died within the 28 days after infusion, duration of exposure will be censored at the date of death.
- Only complete dates will be used when calculating duration of exposure.
- Summary statistics will be produced for the duration of exposure.
 - NOTE: subjects from the parent study BEL112341 received SC belimumab prior to joining BEL14333. Their total duration to exposure is the sum of the exposure to both IV and SC (see details of exposure calculation for SC belimumab below).
- Summary statistics of the total number of infusions.
 - O Additionally, the total number of infusions will also be summarized using counts and percentages using the following categories: 1 to 9, 10 to 19, 20 to 29, 30 to 39, 40 to 49, 50 to 59 and >60 (if applicable).

NOTE: for BEL112341 subjects only. The extent of exposure to SC belimumab during the parent study BEL112341 prior to joining BEL114333, will be assessed by examining the duration of exposure to SC belimumab in days and the total number of injections a subject received. First and last injection dates will be used, regardless of any intermittently missed injections.

• SC belimumab was administered weekly by injection. Duration of exposure to SC belimumab (in days) will be calculated for each subject, as:

Extent of Exposure (days) =

Date of last exposure to SC treatment +7 – Date of first exposure to SC treatment where

- the first SC belimumab dose either occurred during the DB portion of the parent study BEL112341 (for subjects randomized to belimumab in BEL112341) or the open-label portion of the parent study BEL112341 (for subjects randomized to placebo in BEL112341).
- the last SC belimumab dose occurred during the open-label portion of BEL112341 for everyone.
- Only complete dates will be used when calculating duration of exposure.
- Summary statistics will be produced for the total number of injections.
 - Additionally, the total number of injections will also be summarized using counts and percentages using the following categories: 1 to 23, 24 to 76, and >76 (if applicable).

7.2. Overview of Planned Adverse Event Analyses

Table 8 provides an overview of the planned Adverse Event analyses, with full details of data displays being presented in Appendix 12: List of Data Displays. Data from all subjects as one treatment belimumab group will be presented.

Table 8 Overview of Planned Adverse Events Analyses

Endpoint		Absolute	
	Sum	Summary I	
	T	F	L
AE Summary by Year Interval	Υ		
Cumulative AE Incidence Over Time		Υ [4]	
Adverse Events by SOC			
AE by SOC	Υ		
Serious AE by SOC	Υ		
Severe AE by SOC	Υ		
Study Drug Related AE by SOC	Υ		
AE Leading to PD of Study Drug or WD from Study by SOC	Υ		
Adverse Event Rates by SOC			
AE Rate by SOC	Υ		
Serious AE Rate by SOC	Υ		
Severe AE Rate by SOC	Y		
Study Drug Related AE Rate by SOC	Υ		

Endpoint		Absolute		
		Summary		
	Т	F	L	
AE Leading to PD of Study Drug or WD from Study Rate by SOC	Υ			
Adverse Events by SOC & PT				
AE by SOC & PT	Υ		Υ [2]	
Serious AE by SOC & PT	Υ		Y [2]	
Severe AE by SOC & PT	Υ			
Study Drug Related AE by SOC & PT	Υ			
AE Leading to PD of Study Drug or WD from Study by SOC & PT	Υ		Y [3]	
Subject Numbers by Individual AE by SOC & PT			Υ [2]	
Relationship between AE SOC, PT and Verbatim Text			Υ [2]	
Adverse Events by SOC & PT (Subgroups)				
AE by Age Group (< 65 vs ≥ 65 Years), SOC and PT	Y (x2) [1]			
AE by Gender (Male vs Female), SOC and PT	Y (x2) [1]			
AE by BL SELENA SLEDAI (≤ 9 vs ≥ 10), SOC & PT	Y (x2) [1]			
Adverse Events: Non-Serious, Serious & Fatal Serious by SOC & PT				
Fatal Serious Adverse Events			Y [2]	
Non-Fatal Serious Adverse Events			Υ [2]	
Reason for Considering as a Serious Adverse Event			Υ	
Most Common (≥ 10%) Non-Serious Drug Related Adverse Events	Υ			
Most Common (≥ 2%) Serious Drug Related Adverse Events	Υ			
Common (≥ 5%) Non-Serious Adverse Events by SOC and PT (FDAAA)	Υ			
Serious Adverse Events by SOC and PT (FDAAA)	Υ			
Adverse Events by PT				
AE by PT	Υ			
Serious AE by PT	Υ			
Severe AE by PT	Υ			
Study Drug Related AE by PT	Υ			
AE Leading to PD of Study Drug or WD from Study by PT	Υ			
Adverse Events by Maximum Severity				
AE by SOC & Maximum Severity	Υ			
AE by SOC, PT & Maximum Severity	Υ			

NOTES:

- BL = Baseline, PD = Permanent Discontinuation, WD = Withdrawal, T = Table, F = Figures, L = Listings, Y = Yes display generated, (xN) = Number of separate displays generated.
- Summary = Represents TFL related to any summaries (i.e. descriptive statistics) of the observed raw data.
- Individual = Represents FL related to any displays of individual subject observed raw data.
- [1] Separate displays generated for each level of the subgroup.
- [2] Listing generated by SOC, PT and Verbatim Term.
- [3] Listing generated for AE results in study drug discontinuation.
- [4] Kaplan-Meier figure showing each AE category (all, related, serious, severe).

7.2.1. Adverse Events

• Data from all subjects as one belimumab group will be summarised.

- All adverse event tables will show the data by year interval at the start of an AE, and include a summary over the total post-baseline period. Year interval is defined in Appendix 2: Assessment Windows.
- Any AEs that started prior to the first IP administration in the parent study will not be reported. See Section 6.2, footnote 4 in Table 4 for relevance for such AEs as past medical history terms. Only treatment-emergent adverse events will be summarised.
 - o Treatment-emergent AEs are defined as follows:
 - AEs that started on or after the first dose of belimumab treatment.
 - For those subjects who were randomised to placebo in the parent study, ongoing AEs that started before the first open-label belimumab dose (in either BEL112341 open-label extension or BEL114333) and worsened (severity, seriousness, relatedness) at any point during the open-label treatment.
 - Ongoing AEs that started before the first open-label belimumab dose which
 did not worsen during the open-label treatment (for those subjects who were
 randomised to placebo during the parent study) will not be considered
 treatment-emergent, but will be listed.
- Listings will be generated by the parent randomized treatment group (see Table 8). All treatment-emergent AEs as defined above will be listed plus any ongoing AEs that started before the first belimumab dose (for subjects randomised to placebo in the parent study) that were not considered treatment-emergent. AEs that started in each parent study will be flagged.
- The hierarchical relationship between MedDRA SOCs, PTs and verbatim text will be displayed as a listing for all AEs.
- Adverse events in BEL114333 will be coded to the current MedDRA dictionary version at the time of study reporting (version 22.0).
 - NOTE: the same version of the MedDRA dictionary which was used at the time of reporting the parent studies will be used for this current reporting (BEL113750, version 21.1; BEL112341, version 18.0). Any major coding discrepancies between different versions of MedDRA can be addressed in a CSR appendix, if necessary.

7.2.2. Adverse Event Summaries

- An overall summary of AEs will be presented showing the number (%) of subjects with at least one of the following: AE, related AEs, SAE, severe AE, AE resulting in study treatment discontinuation, and deaths.
- The number of events and the number (%) of subjects who had at least one treatmentemergent AE will be summarized for each category of AE listed in Table 9.

Table 9 Adverse Events Categories

AE's	Summary Category
------	------------------

	By SOC	By SOC & PT	By PT
All	YES	YES	YES
Serious	YES	YES	YES
Study Drug Related	YES	YES	YES
Severe	YES	YES	YES
Leading to permanent discontinuation of study	YES	YES	YES
Non-Serious Drug Related		YES	
Serious Drug Related Adverse Events		YES	

SOC = System Organ Class, PT = Preferred Term

- The table for AEs by SOC and PT will be repeated for subgroups. See Appendix 8: Examination of Covariates, Subgroups & Other Strata for more details.
- The tables for AEs by SOC will also be reported for event rates (see below for derivation).
- Summaries of AE incidence, by SOC and maximum severity will also be provided. For these displays, the number (%) of subjects will be summarized as mild, moderate or severe, based on the maximum severity observed across all PTs within the SOC for a given subject. AEs that have missing severity will be excluded from the summaries.
- A Kaplan-Meier figure of cumulative incidence (at least one) of treatment-emergent AE by category (all, related, serious, severe) will be created relative to the first dose of belimumab and censored at the last visit date/contact.
- Listings of AEs will be presented (see Table 8). A listing of AEs in the Infections and Infestations SOC for those subjects with a Grade 3 or Grade 4 IgG toxicity at baseline and/or at any time post-baseline, will also be produced.

Adverse Event Rates

• The event rate will be calculated as the number of events per 100 person-years. The last contact date for AE reporting is the date of the latest scheduled visit where AE/SAE were assessed, as appropriate, up to the 16 week FU visit.

	Event Rate = 100* Number of Events / Subject Years		
Overall Subject Years	\(\sum_{\text{All Subjects in Population}} \) [(\text{Last Contact Date} - 1st Belimumab Treatment Date + 1)] \\ 365 \] NOTE: This will be the denominator for the "Any Time Post Baseline" column.		
Subject Years in Year k	∑ All Subjects in Population (End of Interval Day – Start of Interval Day + 1) 365		

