8.1.3. Analysis of Safety Variables

AEs will be graded for severity by the investigator using Adverse Event Severity Grading Tables ([Appendix 6](#)) or the grades in Section 6.3.4, as appropriate. The frequency of AEs will be tabulated by MedDRA system organ class and preferred term and by treatment groups, according to the treatment group that the subjects were assigned to during randomisation in the BEL113750 or C1115 study. Additional analysis may be performed based on event rates adjusting for subject-years on study agent. The number of subjects with AEs and the incidence rate of AEs will be summarised in each 6-month time interval. AEs will also be summarised by MedDRA SOCs and preferred terms for those that are considered to be at least possibly related to study agent and those that are considered to be severe (Grade 3 and Grade 4). Discontinuations due to AEs will be summarised.

The frequency of laboratory abnormalities will be tabulated by treatment group. Laboratory values will be assessed for significant changes from baseline. Laboratory toxicity will be graded using Adverse Event Severity Grading Tables when possible. Shift tables will be used to determine if subjects move from normal to abnormal during the course of the study. Shifts of ≥ 2 grades and Grade 3 or Grade 4 laboratory abnormalities will be summarised.

Immunogenicity (anti-belimumab antibodies) will be summarized at baseline and during treatment and follow-up.

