1. REPORTING & ANALYSIS PLAN SYNOPSIS

Overview	Key Elements of the RAP
Purpose	The purpose of this RAP is to describe the planned analyses and output to be included in the Clinical Study Report for Protocol BEL114333, which was a continuation study of intravenous (IV) belimumab in Japan and Korea subjects with systemic lupus erythematosus (SLE) who completed the Phase III study BEL113750 in Northeast-Asia (China, Japan, Korea) or who completed the Phase III subcutaneous (SC) open-label extension of HGS1006-C1115 (Japanese subjects only).
	 In this document, HGS1006-C1115 is referred to as GSK study number BEL112341.
	 The complete results for all countries for study BEL112341 (using the SC formulation) and BEL113750 DB study have been previously reported.
	The study (BEL114333) included Japan and Korea, while the OL extension of study BEL113750 included China, of which the study design was similar. Thus, the reporting of OL data will be similar for both studies.
	 Due to process changes in China, the clinical trial permit for a separate OL extension was not available in time for China double-blind subjects to smoothly transition into study BEL114333 without interruption.
	 Per protocol amendment 3, study BEL114333 was extended to allow Japanese subjects to enter, who had completed the 6 month OL extension of BEL112341, after receiving 52 weeks of blinded SC treatment on study BEL112341.
	The BEL114333 study RAP is intended to describe the evaluation of the long-term safety and efficacy of belimumab in subjects with SLE in Japan and Korea.
Protocol	The BEL114333 RAP is based on the following study documents:
	Protocol amendment 3 (Dated: 16/MAY/2014) of study BEL114333 (GSK Document No. YM2010/00145/03).
	Final Case Report Form (eCRF) Version 3 (dated: 17/NOV/2017).
	 Program Safety Analysis Plan (PSAP) for GSK1550188 Version 6 (October 02 2018). Note: for reporting purposes the most current version of the PSAP and associated MedDRA version at the time of the database release (DBR) will be used. Sections of the PSAP that are relevant to reporting are given in the BEL114333 RAP, Appendix 10: PSAP Sections for AESI Reporting.
Primary Objective	The primary objective of BEL114333 is to evaluate long-term safety and tolerability of belimumab in subjects with SLE in Japan and Korea.
Primary Endpoint	Multiple safety endpoints (SAEs, AEs, AEsls, haematology and clinical chemistry parameters, immunogenicity, vital signs).

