2. SUMMARY OF KEY PROTOCOL INFORMATION

2.1. Changes to the Protocol Defined Statistical Analysis Plan

Changes from the originally planned statistical analysis specified in the protocol are outlined in Table 1.

Table 1 Changes to Protocol Defined Analysis Plan

Protocol	Reporting & Analysis Plan		
Statistical Analysis Plan	Statistical Analysis Plan	Rationale for Changes	
Study Completion Status	-		
Section 3.1. Study Design Study completion is defined as: IV belimumab becomes commercially available in the respective countries. Upon the decision of the sponsor to close/terminate the study.	Definition has been revised to include "the subject transferred to a different protocol".	The BEL114333 protocol intent was to include this additional criterion. Similar definition is contained within the BEL113750 OL (China only) Phase of the protocol.	
Safety			
Section 8.1.3 Safety The frequency of AEs will be tabulated by treatment groups, according to the treatment assignment during the respective DB phase of study BEL113750 or BEL112341 (C1115).	Although the adverse events in this section were initially intended to be summarised by parent study randomised treatment groups, the safety data will actually be shown as one total belimumab group.	Similar approach to other Long- Term Continuation (LTC) studies, allowing meaningful comparisons between study BEL114333 and the LTC studies.	
Section 8.1.3 Safety The number of subjects with AEs and the incidence rate of AEs will be summarised in each 6-month time interval.	Adverse events will be summarised by year interval.	For consistency with the LTC studies.	
Section 8.1.3 Safety	AE of Special Interest (AESI) will also be summarised.	AESI (serious and non-serious) of scientific and medical interest specific for GSK are being reported across the Benlysta program.	
Section 8. Data Analysis and Statistical Considerations. Immunogenicity and B cell marker data collected at the 6-month post-treatment visit will be reported separately as an addendum to the clinical study report.	Not required.	The data base will be locked once all subjects have completed their last visit of BEL114333. All data will be included in the BEL114333 CSR.	

Protocol Reporting & Analysis Plan		
Statistical Analysis Plan	Statistical Analysis Plan	Rationale for Changes
Efficacy		- tuttonalo loi onango

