2.2. Study Objective(s) and Endpoint(s)

Objectives	Endpoints	
Primary Objectives	Primary Endpoints	
Evaluate long-term safety and tolerability of belimumab in subjects with SLE in Japan and Korea	The endpoints below will be used to assess this study objective.	
	Adverse events (AEs)	
	 Frequency and percentage of subjects with events. Event rates adjusting for person-years on study agent. Laboratory Parameters Observed and Change from Baseline by visit. Laboratory reference shifts from baseline by visit. Laboratory toxicity worsening of at least two grades from baseline by study year Grade 3 or 4 laboratory abnormalities by visit and study year. 	
	Immunogenicity	
	Immunogenic response (anti-belimumab anti-bodies) by visit and study year.	
	Biomarkers	

[figure not shown]
Objectives	Endpoints
Coonday Objectives	 Percent change from baseline in immunoglobulins, auto-antibodies, and complement levels by visit. Immunoglobulin values below the lower limit of normal by visit and study year. Percent change from baseline in absolute B cell subsets.
Secondary Objectives	SRI and Other Secondary Endpoints
Evaluate the long-term efficacy of belimumab in subjects with SLE in Japan and Korea	SRI response rate at each scheduled visit when complete efficacy evaluations occur (e.g., Week 24 and Week 48 for each year). An SRI response is defined as
	 ≥4 point reduction from baseline in SELENA SLEDAI score, AND
	No worsening (increase of <0.30 points from baseline) in Physician's Global Assessment (PGA), AND
	 No new BILAG A organ domain score or 2 new BILAG B organ domain scores compared with baseline at the time of assessment.
	 Percent of subjects with ≥4 point reduction from baseline in SELENA SLEDAI score assessed every 24 weeks Percent of subjects with No Worsening in PGA compared
	to baseline (added to the RAP)
	Percent of subjects with No new BILAG A organ domain or 2 new BILAG B organ domain scores compared to baseline (added to the RAP)
	 Number of days of daily prednisone dose ≤ 7.5 mg/day
	and/or reduced by 50% from baseline over time.
	Time to first severe SLE Flare Index (SFI) flare assessed over time.
	Other Efficacy Endpoints
	Disease Activity
	Absolute change and percent change from baseline in SELENA SLEDAI (added to the RAP)
	Change in Systemic Lupus International Collaborating Clinics (SLICC)/ACR Damage Index assessed every 24 weeks.
	SLICC/ACR Damage Index Worsening from baseline (added to the RAP).

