• A complete BEL113750 database extraction will be performed (because the DB data will be used in the open-label analyses). Note, there are differences between the prior DB data extraction by a different vendor/format and the open-label data. The complete extraction will enable all the data to be compatible.

The complete extraction will be able to include any additional parent study information (e.g., SAEs, concomitant meds) entered by sites at any time from the start of the parent study, and will be included in aggregate reporting.
 Note any additional SAEs will also be mentioned separately in the open-label phase CSR.

The same database captures data for BEL114333. Similarly, the BEL114333 sites had the ability to also change data pertaining to the parent study BEL113750, per the above

- From the complete database, a selected data extraction of the BEL114333 data will be performed
- The DB data for Japan and Korea subjects will be extracted from the complete BEL113750 data (previously used for the BEL113750 China OL analysis).

Lastly, the BEL112341 Japan subjects who entered BEL114333 will have all relevant data extracted from the complete BEL112341 database.

All relevant belimumab data from the parent studies and study BEL114333 will be aggregated.

Unless otherwise stated, the following statistics will be used to summarise the data:

- Continuous Variables: n, mean, standard deviation (SD), median, 25th & 75th percentiles, minimum and maximum.
- Categorical Variables: n, frequency counts and percentages.

Unless otherwise stated, the following rules will be implemented:

- Summaries by Visit: Only scheduled visits will be presented (i.e. that correspond to the timings of the open-label visits for BEL114333). Otherwise data not shown here will be displayed in listings, and used in derivations such as "any time post-baseline" summaries for laboratory data, time to event, etc. Exit visits will be slotted to the next 6 monthly scheduled visit for that year for efficacy endpoints (or next 12 monthly scheduled visit for SLICC). Otherwise, data will be summarised per the nominal visit.

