- Due to the additional 6 month OL extension for SC subjects entering BEL114333, there is a 6 month off-set in the data capture between the parent studies. As a result, for SLICC, immunoglobulins and B cell subsets, captured on an annual basis in BEL114333, the data captured at each analysis visit stratifies by parent study. As such these endpoints will be tabulated by parent study, and the data will not be aggregated.
- Summaries by belimumab Treatment: Data will be mapped to the year by windowing starting at the time of first belimumab treatment.

The GlaxoSmithKline group of companies

BEL114333

- Listings: If endpoints reported, data will be presented in listings as required.
- Figures: error bars will be displayed.

Unless otherwise stated, no imputation for missing values will be conducted.

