7.3.1. Adverse Events of Special Interest

AESI have already been identified by the GSK Safety Review Team (SRT). This information will be provided for analysis purposes via an adjudication spreadsheet, and therefore, does not need to be re-derived from the raw data. For a broader description, see Appendix 10: PSAP Sections for AESI Reporting.

The reporting of AESIs is defined below.

An overall summary of the incidence of AESI will be tabulated, and presented by study year and "any time post-baseline". Rate of events per 100 person-years will also be reported. Further summaries of the preferred terms assigned to each AE special interest category will be provided.

A listing of all AESIs will be produced.

The categorizations for the adverse events of special interest groups are:

Malignant Neoplasms

- Malignancies Excluding non-melanoma skin cancer (NMSC)
- Malignancies Including NMSC
 - Solid Tumour
 - Hematologic
 - Skin (All)
 - NMSC
 - Excluding NMSC
- Tumours of unspecified malignancy adjudicated as malignant per GSK

Post-Infusion Systemic Reactions (PISR)

- PISR per Anaphylactic Reaction Customized MedDRA Query (CMQ) narrow search
- PISR per Anaphylactic Reaction CMQ broad search
- PISR per Anaphylactic Reaction CMQ algorithmic search
- Serious Anaphylaxis per Sampson Criteria per GSK adjudication
- Serious Acute PISR/Hypersensitivity per GSK adjudication
 - Serious Acute PISR Excluding Hypersensitivity per GSK adjudication
 - Serious Acute Hypersensitivity Reactions per GSK adjudication
- Serious Delayed Acute Hypersensitivity Reactions per GSK adjudication
- Serious Delayed Non-Acute Hypersensitivity Reactions per GSK adjudication

All Infections of Special Interest (All and Serious, separately)

- All opportunistic infections (OI) per GSK adjudication
- OI per GSK adjudication excluding Tuberculosis and Herpes Zoster
- Active Tuberculosis
 - Non-Opportunistic
 - Opportunistic
- Herpes Zoster
 - Non-Opportunistic
 - Opportunistic
 - Recurrent
 - Disseminated
- Sepsis

Depression*/suicide/self-injury (All and Serious, separately)

- Depression* (excluding suicide and self-injury)
- Suicide/self-injury
- Serious suicide/self-injury per GSK adjudication
 - Suicidal Behaviour
 - Completed Suicide
 - Suicidal Ideation

Self-injurious Behaviour without Suicidal Intent

Deaths

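### AE and AESI rates per 100 person-years, one of several listed primary safety endpoints, are planned without any measure of precision, which leaves rare-event and zero-event rows hard to read

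*SAP*

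**What the plan says.** The primary objective is long-term safety and tolerability. SAP 2.2 lists among the primary endpoints, after the frequency and percentage of subjects with events, "Event rates adjusting for person-years on study agent". SAP 7.2.2 gives the calculation: "The event rate will be calculated as the number of events per 100 person-years". The denominator is every subject's follow-up from first belimumab dose to last contact for AE reporting. SAP 7.3.1 applies the same measure to AESIs: "Rate of events per 100 person-years will also be reported".

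Nothing in these sections adds an interval. The SAP 5.1 defaults do not supply one: "Categorical Variables: n, frequency counts and percentages". The other default, "Figures: error bars will be displayed", concerns figures, and SAP 11.12.5 lists no figure of AE or AESI rates. The titles of Tables 2.12 to 2.16 (AE rates) and 2.48 to 2.55 (AESI rates) name only a rate per 100 person-years. Layouts are in a separate shell document (SAP 11.13).

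SAP 2.4 rules out formal hypothesis testing, and Protocol 8 states that no sample size was calculated.

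**The concern.** With no test and no concurrent control, the safety conclusion rests on the estimates, and an estimate from few events says little unless its uncertainty is shown. This matters most for the AESIs. Protocol 1.3.1 puts malignancy (excluding non-melanoma skin cancer) at 0.4% and anaphylaxis below 1% in earlier trials, and SAP 7.3.1 divides the AESI groups into many sub-categories. Some rows may well be empty. A printed 0.0 can then be taken as absence of risk when the data only bound the risk from above.

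A second feature decides which interval is suitable. The rate counts events, not subjects. Under the algorithmic search in SAP Appendix 10 (Section 15.2), once one event at an infusion qualifies, all events in the four term categories linked to that infusion are counted. One clinical reaction can therefore add several events to the numerator.

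**Working it through.** **Inputs.** The documents state no expected event count, precision or total person-years, so there is no figure of the plan's own to reproduce. They give 25 subjects from the subcutaneous parent study (SAP 2.1, Table 1) but not the number from BEL113750. Person-years (PY) are therefore an assumption: 200, 400 or 600.

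**Formula.** For x events in PY person-years, the rate is 100·x/PY. The exact two-sided 95% Poisson limits are:

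- lower = 100 · [χ²(0.025; 2x)/2] / PY, taken as 0 when x = 0
- upper = 100 · [χ²(0.975; 2x+2)/2] / PY

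**Zero events.** χ²(0.975; 2)/2 = −ln(0.025) = 3.689. The upper limit is 100 × 3.689/200 = 1.84, 100 × 3.689/400 = 0.92 and 100 × 3.689/600 = 0.61.

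**Rates per 100 PY with exact 95% limits**

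| Events | 200 PY | 400 PY | 600 PY |
|---|---|---|---|
| 0 | 0.00 (0 to 1.84) | 0.00 (0 to 0.92) | 0.00 (0 to 0.61) |
| 1 | 0.50 (0.01 to 2.79) | 0.25 (0.01 to 1.39) | 0.17 (<0.01 to 0.93) |
| 3 | 1.50 (0.31 to 4.38) | 0.75 (0.15 to 2.19) | 0.50 (0.10 to 1.46) |

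Whatever the person-years, the upper limit is 5.57 times the estimate with one event and 2.92 times with three.

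**How ordinary an empty row would be.** The chance of no event is exp(−rate × PY/100). At an assumed true rate of 0.5 per 100 PY it is exp(−1) = 37% at 200 PY, exp(−2) = 14% at 400 PY and exp(−3) = 5% at 600 PY.

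**Year-interval columns.** SAP 11.2.1 expects few subjects beyond six years. With an assumed 25 or 50 PY in a sparse interval, zero events has an upper limit of 14.76 or 7.38. Limits that wide add little, so the any-time column is the one that matters.

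**Repeat events.** If clustering within subjects multiplies the variance of the event count by 2 or 4 (assumed), an approximate log-scale half-width at 20 events is 1.96·√(2/20) = 0.62 or 1.96·√(4/20) = 0.88. The Poisson value is 1.96·√(1/20) = 0.44. Poisson limits on total events would then be too narrow by a factor of √2 or 2. In a zero-event row nobody leaves the risk set early, so the first-event denominator equals the all-events denominator and the limits above apply to both.

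**The case against.** The case against is that the plan is descriptive throughout and the missing intervals hide nothing. Much of this stands.

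- A reader might take these rates for the primary safety result. They are not: the SAP synopsis names multiple safety endpoints, and Protocol 8.1.3 made rates optional ("Additional analysis may be performed based on event rates adjusting for subject-years on study agent").
- A reader might infer that the SAP's cross-study aim fails without intervals. The phrase "allowing meaningful comparisons between study BEL114333 and the LTC studies" in SAP 2.1 explains why AE data are pooled into one belimumab group. It names neither rates nor AESIs, and no formal cross-study comparison is planned.
- A reader might conclude that the rates cannot be interpreted at all. SAP 7.2.2 plans event and subject counts for AEs, and the overall denominator is common to all rows. Limits on the all-events rate can therefore be rebuilt from any non-zero row that shows its event count. Table 1.3 also gives person-years, though up to the 6-month follow-up rather than the 16-week visit that closes AE reporting.
- A reader might infer that safety is treated worse than efficacy. Error bars are a general rule for figures, and the SRI proportions (8.1.1) and flare rates (8.2.5) have no stated interval either.
- A reader might expect most AESI cells to hold two events or fewer. The documents give no expected counts.

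Repeat counting is also partly controlled. AESI incidence has its own tables (2.39 to 2.47), events spanning the parent study and this one are counted once (SAP 11.3.1), and a malignancy flagged more than once is adjudicated as one event (Appendix 10, Section 16.1).

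What remains is that rebuilding limits is left to the reader. It cannot yield a first-event rate, because time to first event is not in the planned AESI summaries. The Kaplan-Meier figure of first events covers all, related, serious and severe AEs, not AESIs.

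**Conclusion.** The point holds as an inexpensive improvement to an estimation-only safety report; it does not show that any planned result is wrong. The SAP text defines AE and AESI rates as point estimates with no precision. For a zero-event row the missing information is an upper limit of 1.84, 0.92 or 0.61 per 100 person-years at 200, 400 or 600. For one to three events the rate does not read as no risk, but its upper limit is about three to six times the estimate.

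The zero-event limits depend on assumed person-years. The multiples depend only on the event count and on independent events. The finding is limited to the SAP text, since the shells might already hold an interval column; if they do, the text should still specify the method.

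**What to change.** In the any-time post-baseline column of the AESI rate tables (2.48 to 2.55, or at least the overall categories in 2.48), add a first-event incidence rate: subjects with a first event divided by person-years to first event or censoring. Give its exact Poisson 95% interval, zero-event rows included. Show it beside the existing all-events rate as a separate, labelled quantity, so that no interval sits next to an estimate it does not describe.

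In the general AE rate tables (2.12 to 2.16), where repeat events are common, use the same first-event rate and interval, or a subject-clustered (robust or bootstrap) interval for the all-events rate. Do not put exact Poisson limits on total events.

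State in SAP 7.2.2 and 7.3.1 that all intervals are descriptive and unadjusted for multiplicity.

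No new data, visits or hypotheses are needed. The cost is deriving first-event denominators for each category or term shown, wider tables, and limits that look less reassuring than a bare 0.0.
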